Study Identification

ClinicalTrials.gov ID: NCT03119025

Unique Protocol ID: IFCI-04/10/2015

Brief Title: Autologous Dendritic Cell Vaccine for Treatment of Patients with Chronic HCV-Infection

Official Title: Safety/Efficacy of Vaccination with Autologous Dendritic Cells Pulsed with Recombinant HCV-Antigens (Core and NS3) for Treatment of Patients with Chronic HCV-Infection

The protocol was approved by the Ethics Committee of the Institute of Fundamental and Clinical Immunology (approval number: no 88, 04/10/2015)

April 10, 2015

Statistical Analysis Plan

Data will be analyzed using Statistica 9.0 software. The results of statistical analysis will be presented as median and interquartile range. The Mann–Whitney test (for independent samples; p_U) and Wilcoxon test (for dependent samples; p_W) will be applied, and differences with p less than 0.05 will be considered statistically significant. Correlation analysis will be conducted by Spearman's rank-order correlation (R_S).

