Study Identification

Unique Protocol ID: IFCI-04/10/2015

Brief Title: Autologous Dendritic Cell Vaccine for Treatment of Patients with Chronic HCV-Infection

Official Title: Safety/Efficacy of Vaccination with Autologous Dendritic Cells Pulsed with Recombinant HCV-Antigens (Core and NS3) for Treatment of Patients with Chronic HCV-Infection

The protocol was approved by the Ethics Committee of the Institute of Fundamental and Clinical Immunology (approval number: no 88, 04/10/2015)

Study Description

Purpose/Brief Summary:

Clearance of HCV infection requires earlyand multi-specific HLA class I restricted CD8+ T cell and class II restricted CD4+ T cell responses to both structural (Core) and non-structural HCV proteins (NS3, NS4A, NS5A, NS5B). Dendritic cells (DCs) are professional antigenpresenting cells that link innate and adaptive immune responses, and play a major role in priming, initiating, and sustaining strong anti-HCV T cell immune responses.

The general objective of this study is to evaluate safety, feasibility and clinical efficacy of therapeutic vaccinationin genotype 1 HCV patients using autologous DCs pulsed with recombinant HCV-antigens (Core and NS3). Expected effects: DC vaccination induces Core/NS3-specific immune response and reduces viral load in patients with chronic HCV-infection.

Condition	Intervention	Phase
Hepatitis C, Chronic	Biological: Autologous monocyte-derived dendritic cells,	Phase 1
	generated in the presence of IFN- α /GM-CSF and pulsed with recombinant HCV Core (1-120) and NS3 (1192-1457)	Phase 2
	proteins.	

Detailed Description:

Hepatitis C virus (HCV) has chronically infected an estimated 170 million people worldwide. People infected with HCV are at risk for developing chronic liver diseases, such as liver cirrhosis and primary hepatocellular carcinoma. It has been estimated that HCV accounts for 27% of cirrhosis and 25% of hepatocellular carcinoma worldwide. Therapy for chronically HCV-infected patients has involved a pegylated interferon-alpha and ribavirin (pegIFN/RBV) and is still the only FDA-approved therapeutic combination. However, this therapy is expensive, non-specific, toxic, and only effective in about 50% of genotype-1 HCV patients.

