An early immune response, represented by the activation of NK cells, the development of vigorous anti-HCV CD4+ and CD8+ T-cell responses, and the appearance of HCV-specific antibodies, is mounted by the host during acute HCV infection and leads to clearance of the virus. However, in the vast majority (\approx 85%) of infected individuals HCV causes a persistent infection. The mechanisms of HCV persistence remain elusive and are largely related to inefficient clearance of the virus by the host immune system.

Although HCV genome is very variable with hundreds of serotypes and six genotypes, several structural (Core) and nonstructural proteins (NS3, NS4A, NS5A, NS5B) are highly conserved among genotypes and subtypes. It is apparent that clearance of hepatitis C infection requires early and multi-specific HLA class I restricted CD8+ T cell and class II restricted CD4+ T cell responses to both structural and non-structural HCV proteins.

DCs are professional antigen-presenting cells that link innate and adaptive immune responses. DCs play a major role in priming, initiating, and sustaining strong T cell responses against pathogen-derived antigens. Therefore DC-based therapy represents a promising immunotherapeutic approach in terms of their propensity to establish anti-HCV adaptive immune responses.

This trial is a prospective, non-blinded, interventional study to determine safety, feasibility and clinical efficacy of therapeutic vaccination in genotype 1 HCV patients using autologous DCs pulsed with recombinant HCV-antigens (Core and NS3). Our previous work has shown that the short-term loading of DCs with recombinant HCV proteins Core (1-120) and NS3 (1192-1457) have no any marked inhibitory effect on maturation and functions of DCs [Oleynik E.A., et al. 2016].

In experimental group thirty patients with chronic hepatitis C (genotype 1) will be vaccinated via intracutaneous injection of monocyte-derived DCs, generated in the presence of IFN- α /GM-CSF and pulsed with recombinant HCV Core (1-120) and NS3 (1192-1457) proteins. The vaccination protocol will includes initiating (one injection per week, no 4) and maintaining (one injection per month, no 6) courses with subsequent 6-month of follow up.

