The safety will be determined by the evaluation of the number of participants with the adverse events. Liver safety will be assessed by blood analysis and Ultrasound. Patients will be monitored in a 2 months (after completing of initiating course), 7 months (after completing of maintaining course) and 13 months (in a 6 months post-vaccination follow-up).

Conditions

Conditions: Hepatitis C, Chronic; Liver Diseases; Hepatitis, Viral, Human; Hepatitis, Chronic; Virus Diseases.

Keywords: Dendritic Cells; DC-based Vaccines; Chronic HCV Infection; Antigen-Specific T cell response; Recombinant HCV-Core antigen; Recombinant HCV-NS3 antigen.

Study Design

Study Type: Interventional Primary Purpose: Treatment Study Phase: Phase 1/Phase 2 Intervention Model: Single Group Assignment Number of Arms: 1 Masking: No masking Enrollment: 30

Arms and Interventions

Arms	Assigned Interventions
Experimental: Autologous DC-vaccines	Biological/Vaccine: Autologous DC-vaccines
Thirty patients with chronic hepatitis C (genotype 1) will receive the initiating and maintaining courses of autologous monocyte-derived dendritic cells, generated in the presence of IFN- α /GM-CSF and pulsed with recombinant HCV Core (1-120) and NS3 (1192-1457) proteins.	Patients will be vaccinated via intracutaneous injection of autologous DCs (5×10^6) combined with adjuvant subcutaneous injection of recombinant hIL-2 (250 000 IU). Initiating course: one vaccination per week, during 1 month. Maintaining course: one vaccination per month, during 6 month. Patients will be monitored in a 2 months (after completing of initiating course), 7 months (after

completing of maintaining course) and 13 months (in a 6 months post-vaccination follow-up).

Outcome Measures

Primary Outcome Measure:

1. Number of Participants with Severe Adverse Reactions and/or With Abnormal Clinical Laboratory Values That Are Related to Treatment

[Time Frame: From enrollment and up to 13 months]

Frequency of severe adverse reactions will be evaluated from enrollment and up to 13 months. Liver safety by blood analysis (ALT, AST, GGT, Total and conjugated bilirubin, platelets, ESR, etc) and Ultrasound will be assessed from enrollment and up to 13 months (= baseline, 2, 7 and 13 months after 1-st vaccination).

Secondary Outcome Measure:

2. Number of Participants with Virological Response According to HCV RNA Viral Load [Time Frame: Baseline, 2, 7 and 13 month after 1-st vaccination]

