Virological response in patients receiving DC-vaccinations is defined as change from baseline in HCV RNA viral load by at least 1 log at 2, 7 and 13 month after 1-st vaccination. Plasma level of HCV RNA will be measured by Real-Time Reverse Transcription-Polymerase Chain Reaction (RT-PCR)

3. Number of Participants Who Have Developed or Increased Anti-Viral Immune Response According to T-cell proliferation

[Time Frame: Baseline, 2, 7, and 13 months after 1-st vaccination]

Change from baseline in T-cell proliferative response to HCV Core and NS3 proteins at 2, 7 and 13 month after 1-st vaccination. T-cell proliferation will be evaluated using radiometry based on 3H-thymidine incorporation.

4. Number of Participants Who Have Developed or Increased Anti-Viral Immune Response According to $IFN-\gamma$ production

[Time Frame: Baseline, 2, 7, and 13 months after 1-st vaccination]

Change from baseline in T-cell IFN- γ -producing response to HCV Core and NS3 proteins at 2, 7 and 13 month after 1-st vaccination. Production of IFN- γ will be measured by ELISA kit

Eligibility

Minimum Age: 18 Years Maximum Age: 65 Years Sex: All Accepts Healthy Volunteers: No

Criteria:

Inclusion Criteria:

- Age 18 to 65 Years (Adult)
- Chronic hepatitis C (genotype 1b)
- HCV-positive patients
- Plasma HCV RNA level $\geq 10^4$ IU/ml
- Liver fibrosis (METAVIR Score 0-III)

- Patients must be able totolerate all study procedures
- Patients must be willing to voluntarily give written Informed Consent to participate in the study before any procedures are performed
- Patients must be willing to be available for all baseline, treatment and follow-up examinations required by protocol

Exclusion Criteria:

- Co-infection with hepatitis B, A, D, E, cytomegalovirus or Epstein-Barr virus
- Liver cirrhosis (METAVIR Score IV)
- The high degree of hepatitis activity (ALT and/or $AST \ge 10$ ULN)
- Received any vaccine within a month prior to study entry
- A history of diabetes
- Psychiatric disorders
- Renal dysfunctions
- Hemodynamic or respiratory instability
- HIV or uncontrolled bacterial, fungal, or viral infections
- Autoimmune diseases
- Pregnancy
- Malignancy
- Participation in other clinical trials

Contacts/Locations

Central Contact: [name] [contact] Email: [contact]

Central Contact Backup: [name] [contact] Email: [contact]

Study Chair: [name], PhD

Study Principal Investigator: [name], PhD

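### The primary safety outcome and virological response are participant counts, but no method in the SAP gives a proportion or its uncertainty

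*SAP*

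**What the plan says.** The analysis text of the SAP is one short paragraph. After naming the software it says "The results of statistical analysis will be presented as median and interquartile range". It then lists the Mann–Whitney test for independent samples, the Wilcoxon test for dependent samples, a 0.05 significance level and Spearman correlation.

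The protocol's Outcome Measures section defines the primary outcome as "Number of Participants with Severe Adverse Reactions and/or With Abnormal Clinical Laboratory Values That Are Related to Treatment". It adds that "Frequency of severe adverse reactions will be evaluated from enrollment and up to 13 months" and that "Liver safety by blood analysis (ALT, AST, GGT, Total and conjugated bilirubin, platelets, ESR, etc) and Ultrasound will be assessed" at baseline and at 2, 7 and 13 months. Secondary outcome 2 is "Number of Participants with Virological Response According to HCV RNA Viral Load", and "Virological response in patients receiving DC-vaccinations is defined as change from baseline in HCV RNA viral load by at least 1 log". The visits for this outcome are months 2, 7 and 13.

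The design is a single unmasked group with enrolment of 30. The Detailed Description says "In experimental group thirty patients with chronic hepatitis C (genotype 1) will be vaccinated".

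**The concern.** Each patient either has or does not have a treatment-related severe reaction or laboratory abnormality, and either does or does not reach a 1-log response. Such outcomes call for a count, a denominator and an interval. None of the SAP's methods gives a proportion or says how precise it is.

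The denominator and the missing-result rule are also left open. The protocol points to the vaccinated patients, but it does not say how many of the ten planned injections (4 initiating and 6 maintaining) bring a patient into the analysis. Nor does it say what happens to someone who leaves before month 13 or lacks a laboratory or HCV RNA result.

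Safety is the primary outcome. With 30 patients a zero or near-zero count is quite possible even if the true risk is not small, and nothing in the plan brings that uncertainty into the conclusion.

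**Working it through.** **Inputs.** From the documents: n = 30, one arm, two yes/no outcomes, visits at 2, 7 and 13 months. The documents give no event rate, response rate, safety margin, dropout figure or precision target, so there is no stated figure to reproduce. The event counts, missing counts and viral-load changes below are assumptions.

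**1. The planned summary applied to a yes/no outcome.** Code 30 patients as 0 or 1. With 7 events there are 23 zeros. The upper quartile by linear interpolation sits at ordered position 1 + 0.75 × 29 = 22.75, between the 22nd and 23rd values, both 0. So every count from 0 to 7 gives a median of 0 (quartiles 0 and 0). Some other quartile rules give a value slightly above 0 at exactly 7.

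**2. Precision of the count.** Exact (Clopper–Pearson) 95% limits for k of n are the 0.025 quantile of Beta(k, n − k + 1) and the 0.975 quantile of Beta(k + 1, n − k). For k = 0 the upper limit is 1 − 0.025^(1/n).

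- 0/30: 1 − 0.025^(1/30) = 11.6%
- 3/30 = 10.0% (2.1 to 26.5%)
- 6/30 = 20.0% (7.7 to 38.6%)

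The chance of seeing no events in 30 patients is (1 − p)^30. For assumed true rates of 2%, 5% and 10% it is 0.98^30 = 55%, 0.95^30 = 21% and 0.90^30 = 4%.

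**3. Missing safety data, with no event observed.**

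| Patients with incomplete data (assumed) | Counted as no event | Excluded | Counted as events |
|---|---|---|---|
| 3 | 0/30, upper limit 11.6% | 0/27, upper limit 12.8% | 3/30, upper limit 26.5% |
| 6 | 0/30, upper limit 11.6% | 0/24, upper limit 14.2% | 6/30, upper limit 38.6% |

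Excluding such patients moves the limit little. Counting them as events moves it a lot. The rule therefore needs to be set before the data are seen.

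**4. Missing virology, with six observed responders (assumed).** Missing counted as non-response: 6/30 = 20.0% (7.7 to 38.6%). Observed only: 6/27 = 22.2% (8.6 to 42.3%) with 3 missing, or 6/24 = 25.0% (9.8 to 46.7%) with 6 missing.

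**5. Wilcoxon shift against 1-log responder count.** These answer different questions, and how far they diverge depends on the assumed change. I simulated 20,000 trials of 30 normally distributed paired changes in log10 HCV RNA, with a two-sided signed-rank test at 0.05 (normal approximation). The three entries in each cell are for an SD of change of 0.4, 0.5 and 0.6. The true 1-log rate is Φ((−1 + mean fall)/SD).

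| Mean fall (log10) | True 1-log response rate | Wilcoxon p < 0.05 | p < 0.05 with at most 3 responders |
|---|---|---|---|
| 0.1 | 1.2 / 3.6 / 6.7% | 26 / 18 / 14% | 26 / 17 / 10% |
| 0.3 | 4.0 / 8.1 / 12.2% | 97 / 87 / 74% | 94 / 66 / 31% |
| 0.5 | 10.6 / 15.9 / 20.2% | 100 / 100 / 99% | 61 / 28 / 11% |
| 0.8 | 30.9 / 34.5 / 36.9% | 100 / 100 / 100% | under 1% |

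The divergence is wide around a 0.3 log10 fall and nearly absent at 0.8. No single row describes this trial.

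**The case against.** The protocol already asks for a number of participants and a frequency, gives a 1-log threshold and names the visits. A bare count can be reported without any statistical method, and the median and rank tests suit the continuous data also collected: HCV RNA, liver tests, proliferation and IFN-γ. In an early-phase single-arm study with no stated safety margin, a reader can work out an interval from n and N. All of this stands, and it makes the gap an omission rather than an error. But the reader can do so only if N and the handling of missing results are fixed and reported, and the plan secures neither.

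Three stronger readings are tempting, and the documents support none of them.

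- A reader might infer that the plan cannot deliver its primary result at all. It can deliver a raw count; what it lacks is the proportion, its uncertainty and the rules behind them.
- A reader might infer that a significant Wilcoxon test will be offered as virological response. The SAP assigns that test to dependent samples generally, never says it decides response, and the protocol defines response separately.
- A reader might infer that a 1-log rise would count as response, because the definition says only change. The Brief Summary makes the intended direction plain: "Expected effects: DC vaccination induces Core/NS3-specific immune response and reduces viral load in patients with chronic HCV-infection". Stating a reduction is a tidy-up.

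The missing laboratory threshold, the open-ended list of tests, the absent responder cut-offs for outcomes 3 and 4 and the unnamed Mann–Whitney groups are minor clarifications. The point does not rest on them.

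**Conclusion.** The point holds as a gap that should be fixed. For the primary safety outcome and virological response, the SAP names no method that gives a proportion or an interval, and neither document sets an explicit analysis set or a missing-result rule. The exact limits depend only on the count and the denominator: an event-free result in all 30 patients would still be compatible with a true rate up to 11.6%. The range from 11.6% to 38.6% across missing-data rules rests on an assumed zero observed events and up to 6 patients with incomplete data. The difference between a Wilcoxon shift and a responder count is real in principle, but its size depends on the assumed mean fall and SD. It supports reporting the two separately and nothing more.

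**What to change.** Amend the SAP as follows.

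1. **Primary safety.** Report n/N with an exact (Clopper–Pearson) 95% interval, where N is all patients given at least one vaccination. State the upper limit in any safety conclusion, including when n = 0. Show severe reactions and treatment-related laboratory abnormalities separately and combined. Report how many patients lack complete safety data. In the main result these count as no event unless an event was seen. Add two sensitivity results: one excluding event-free patients with incomplete data, and one counting them as events.
2. **Virological response.** State it as a reduction of at least 1 log10 from baseline. Report n/N with an exact 95% interval separately at 2, 7 and 13 months, with the same N. Fix the missing-result rule in advance, for example missing counted as non-response with an observed-only sensitivity result. Another rule would serve if set beforehand.
3. **Continuous values.** Keep the median, interquartile range and Wilcoxon for paired continuous measurements. Report the shift in log10 HCV RNA and the responder count as answers to different questions.
4. **Minor clarifications.** Settle the laboratory definition and list of tests, the cut-offs for outcomes 3 and 4, and any Mann–Whitney groups before analysis.

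The cost is SAP wording and a short protocol clarification, with no new patients or measurements. The price is a less favourable safety statement and possibly a lower response rate. The sensitivity results also have known biases: excluding event-free patients with incomplete data overstates the event rate if patients without events leave early, and counting them as events is a deliberate worst case.

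### The SAP's p<0.05 rule spans up to 15 inferred efficacy comparisons with no ranking, adjustment or exploratory label, so one isolated favourable result could be reported as a significant immune response

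*SAP*

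**What the plan says.** The SAP's analysis text is one paragraph. It names the Mann-Whitney test for independent samples and the Wilcoxon test for dependent samples, and adds that "differences with p less than 0.05 will be considered statistically significant". Spearman correlation follows in its own sentence, with no threshold. No test is tied to any outcome, antigen or visit.

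The protocol's Study Design section gives "Intervention Model: Single Group Assignment Number of Arms: 1 Masking: No masking Enrollment: 30". Its one primary outcome is safety: "Number of Participants with Severe Adverse Reactions and/or With Abnormal Clinical Laboratory Values That Are Related to Treatment". Three secondary efficacy outcomes follow:

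- **Viral load.** The criterion for response reads "change from baseline in HCV RNA viral load by at least 1 log at 2, 7 and 13 month after 1-st vaccination".
- **T-cell proliferation.** The title is a count, "Number of Participants Who Have Developed or Increased Anti-Viral Immune Response According to T-cell proliferation", but the description speaks of a shift from the baseline value, for each of the two antigens and at each of the three visits.
- **IFN-γ production.** This has the same structure as proliferation: two antigens and three visits.

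Neither immune outcome has a responder threshold. The outcomes are numbered, but the numbers carry no testing priority. The Purpose/Brief Summary names two expected effects: "DC vaccination induces Core/NS3-specific immune response and reduces viral load in patients with chronic HCV-infection".

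**The concern.** The SAP does more than stay silent on multiplicity. It states a positive rule under which any difference below 0.05 earns the word significant. The protocol expects an induced immune response but does not say which assay, antigen or visit would establish it. A favourable p-value for one antigen, in one assay, at one visit could therefore be reported as a statistically significant immune response, in full compliance with the plan. The reader of that report could not tell whether the result was the one the sponsor meant to rely on or the best of a dozen.

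What is at stake is how the secondary efficacy results may be read, above all the immune ones.

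**Working it through.** The documents contain no power, sample-size or familywise error calculation, so there is no figure of the plan's own to reproduce. The only stated error rate is 0.05 per test.

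**Inputs from the documents.** Threshold 0.05 (SAP); 30 patients in one arm (Protocol, Study Design); three post-baseline visits, two immune assays and two antigens (Protocol, Outcome Measures).

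**Assumptions.**
- Tests are two-sided. The SAP does not say.
- Wilcoxon is applied to change from baseline. This is inferred from the outcome descriptions and from Wilcoxon being the only paired test named; the outcome titles are participant counts.
- All 30 patients have data at every visit.
- Visit changes correlate 0.5 to 0.9, and immune readouts correlate 0 to 0.9. The documents give no correlations, so these values are illustrative. For visits, 0.5 is what a shared baseline alone produces when all measurements are independent with equal variance.

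**1. Number of looks.** Immune: 2 assays × 2 antigens × 3 visits = 12, or 2 × 3 = 6 if the antigens are pooled. Viral load: 3. Total: up to 12 + 3 = 15. Mann-Whitney and Spearman analyses are extra, and their number is not stated.

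**2. One test.** The exact signed-rank test at n = 30 (critical value 137) has size 0.0249 in the favourable direction, or 0.0497 two-sided. The nominal favourable rate is 2.5%.

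**3. Ceilings for at least one favourable result with no true change.** If the k tests are independent, the chance is 1 − (1 − 0.025)^k:
- k = 12: 26.2%
- k = 6: 14.1%
- k = 3: 7.3%

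Under any correlation at all it cannot exceed k × 0.025, which is 30%, 15% and 7.5%.

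**4. Simulation.** Exact signed-rank tests at n = 30 on Gaussian changes with no true shift, 40,000 trials per setting. Entries are the chance of at least one favourable p<0.05.

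| Readout corr. | Visit corr. | Immune, 12 looks | Immune, 6 looks | Viral load, 3 looks |
|---|---|---|---|---|
| 0 | 0.2 (outside the assumed range) | 25.2% | 13.5% | 7.1% |
| 0 | 0.5 | 23.1% | 12.6% | 6.5% |
| 0.5 | 0.7 | 16.5% | – | – |
| 0.9 | 0.9 | 8.1% | 6.3% | 4.1% |

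Above 0.9 the figures fall further. With visit, assay and antigen correlations all at 0.95, a normal-statistic run gives 5.9% over 12 looks.

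**5. A stricter success rule.** Suppose both antigens must be favourable in the same assay at the same visit. With uncorrelated readouts the chance is at most 6 × 0.025² = 0.4%. With readout and visit correlations both at 0.9 it is about 3.5% (normal-statistic simulation). High readout correlation with low visit correlation (0.9 and 0.5) is the least favourable mix checked, at about 5%. The result in step 4 therefore depends heavily on the success rule.

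**The case against.** The strongest reply is that 8% to 23% needs a rule the documents do not contain. Nothing in them says that one significant look establishes an immune response. Requiring both antigens to respond, or both an immune and a viral-load effect, is no less faithful to the text. This stands. The percentages are conditional on an any-one-look reading, on inferred tests, on assumed correlations and on two-sidedness. What survives is that the plan does not exclude that reading, because it fixes no success rule and attaches significance to each difference separately.

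Second, efficacy is already secondary to safety, the visits and antigens are listed in advance, and formal error control for immune readouts in a 30-patient, single-arm Phase 1/2 study is largely a matter of preference. This is also fair, and it is why the remedy is a label and full reporting, with no compulsory correction. But the SAP does not call these analyses exploratory, and its wording says the opposite.

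Third, because the outcomes are titled as participant counts and the SAP names no analysis for counts, the 12 Wilcoxon tests may never be run. That uncertainty is real, and the fix covers both forms of reporting.

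A reader might also infer that the 0.05 rule governs the Spearman correlations. The text does not say so: the threshold attaches to differences, and correlation comes in a later sentence without one.

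**Conclusion.** The concern holds as a gap in the stated significance rule. Three unranked secondary efficacy outcomes, at three visits and partly for two antigens, sit under a blanket 0.05 threshold with nothing to order, adjust or label them.

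If a single favourable look sufficed, the immune claim would carry about 8% to 23% over 12 looks, or 6% to 13% over 6, against 2.5%. This is illustrative, within an independence ceiling of 26%, and lower if correlations exceed 0.9.

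Three stronger readings are tempting, and the documents do not support them:
- **That the trial has an 8% to 23% false-positive rate.** The documents define no success rule from which such a rate would follow.
- **That viral load is badly inflated.** Three looks give about 4% to 6.5%, and response has its own 1-log criterion.
- **That the main conclusion is compromised.** The safety primary is unaffected.

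A separate limit is that IL-2 is given with every vaccination and there is no control arm. A genuine before-after change, however small its p-value, cannot be assigned to the cells alone. That is a matter of attribution, which multiplicity adjustment does not address, and the documents give no basis for putting a size on it.

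The sponsor should make the change. Confidence is medium: the documentary gap is certain, and its size is not.

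**What to change.** **SAP wording only.** Replace the blanket rule for efficacy with three statements:

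1. Efficacy p-values (Wilcoxon, Mann-Whitney and any attached to Spearman correlations) are exploratory and unadjusted, and support no confirmatory claim of significance.
2. Every readout, antigen and visit is reported as median change with 95% CI, and each participant count as n/N with exact 95% CI.
3. Before-after changes in one arm given cells plus IL-2 cannot be attributed to the cells alone.

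The cost is a few sentences, with no change to visits, assays or sample size. The downside is that no efficacy result can be called confirmed as statistically significant.

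**Optional, only if the sponsor wants a significance claim.** Before data are examined, name one key visit, apply Holm across the four immune readouts at that visit, and treat viral load as a separate claim at 0.05. Other visits become descriptive. The SAP should then say that error is controlled within each claim only. In simulation, Holm gives 2.6% to 4.8% for the immune claim in either direction. Taking the two claims as independent, the chance of any false result across both is 1 − 0.95 × (1 − 0.026) = 7.5% to 1 − 0.95 × (1 − 0.048) = 9.6%, and it cannot exceed 5% + 5% = 10%.

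This route also costs power. For an illustrative standardised paired change of 0.55 at n = 30, power is 81% at 0.05 but 61% at the strictest Holm step (0.05/4 = 0.0125).
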